X-ray is conducted at Week 4, or when simple X-ray and bone scintigraphy are conducted at Week 8, during observation period, and Week 48 (completion of observation period), date of examination and assessment findings (improvement, unchanged, aggravation of bone morphology, trabecular bone structure and other abnormal findings by simple X-ray, compared with baseline) should be recorded.

When CT and MRI is conducted at baseline, record the findings.

(6) Adverse events

Record the name of an adverse event that developed after the baseline and before completion of observation period, date of onset, seriousness, action taken, outcome, and causal relationship with this drug to be evaluated. Follow up adverse events until recovery as best as possible.

(7) Laboratory test

Conduct general hematology, blood chemistry, and urinalysis at baseline and during observation period and record the test item assessed as abnormal variation compared with baseline in the adverse events section of CRF. Record the laboratory test data of the item assessed as abnormal variation in “Variation of laboratory test data assessed as abnormal variation” section.

8. Items and method of analysis

(1) Analysis population

Conduct analysis for all patients administered this drug.

Conduct analysis of the patients above according to the baseline demographics and pathology.

(2) Demographic factors

Tabulate patients by sex, age, weight, morbid period, prior therapy, concomitant drugs.

(3) Efficacy endpoint

1) Serum ALP, bone metabolism markers

i) Serum ALP

Calculate summary statistics (mean, standard deviation, minimum, maximum) and 95% confidence interval for the excess serum ALP measured at baseline, Week 4, Week 8, during observation period, and Week 48. Conduct one-sample t-test for percent change in excess serum ALP. Show time-course of change at baseline, Week 4, Week 8, during observation period, and Week 48.

*Excess serum ALP: actual value of serum ALP — (maximum of reference value + minimum of reference value)/2

ii) Bone metabolism marker

Calculate the mean and standard deviation for the values measured before and after administration. Conduct one-sample t-test for percent change.

2) Tabulation of pain associated with osseous Paget's disease

Show distribution of pain severity at each time point of baseline, Week 4, Week 8, during observation period, and Week 48.

3) Treatment compliance

Conduct frequency tabulation for treatment compliance during treatment period.

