To observe the efficacy and safety of BENET Tablets 17.5 mg/Actonel Tablet 17.5 mg in patients with osseous Paget's disease up to Week 48 as an all-case surveillance based on the approval conditions.

2. Patients to be included in analyses

(1) Breakdown of patients to be included in analyses

“Patients included in safety evaluation” and “patients included in efficacy evaluation”.

(2) Patients included in safety evaluation

Of the patients from whom a case report form (CRF) is collected, those who satisfy either of the following conditions are excluded from safety evaluation and others are included in safety evaluation.

- i) A patient not administered this drug
- ii) A patient in whom onset of adverse event is unknown
- iii) Of the patients with duplicated enrollment, those who were enrolled later.
- iv) A patient for whom administration was started outside the enrollment period*

* The date of starting administration falls after the enrollment period of January 31, 2016 (on and after February 1, 2016).

(3) Patients included in efficacy evaluation

Of the patients included in safety evaluation, those who satisfy the following conditions are excluded from efficacy evaluation and others are included in efficacy evaluation.

- i) patients from whom the information on efficacy before and after administration was not obtained.

3. Handling of patients

Unless otherwise specified, a patient recorded in a different CRF as a re-administered patient will be tabulated as one patient based on each CRF even if he/she is the same person. When tabulating the same patient as one patient, it should be clarified in “creation method” that tabulation is conducted for “each patient unit”.

4. Data Lock Point

(1) Data Lock Point

Date of starting survey: August 1, 2008

Data Lock Points (DLP) are shown below.

1st: September 30, 2008

2nd: March 31, 2009

3rd: September 30, 2009

4th: March 31, 2010

5th: March 31, 2011

6th: March 31, 2012

7th: March 31, 2013

8th: March 31, 2014

9th: March 31, 2015

10th: March 31, 2016

11th: March 31, 2017

12th: March 31, 2018, re-examination

13th: July 15, 2018, re-examination “(4) Safety analysis 10) Profile Table of serious adverse drug reactions,

11) Profile Table of adverse drug reactions not foreseeable from ‘Precautions’”

5. Tabulation and analysis at each DLP

(1) Patient composition diagram

<Analysis population>

Enrolled patients.

<Preparation method>

- 1) number of study sites
- 2) number of enrolled patients

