All patients in spontaneous reporting, literature, drug use surveillance, special drug use survey, clinical trials, post-marketing clinical trials, and a clinical trial conducted by other pharmaceutical company.

<Preparation method>

Concerning serious adverse drug reactions, number of patients will be calculated for each type of adverse drug reactions (according to SOC and PT) by the timing of onset and outcome category shown in Table (2). In case of several occurrences of the same adverse event/adverse drug reaction (LLT) in a given patient, they will be tabulated as one according to the priority order in 4). Events with the same PT but different LLT will be tabulated as separate events.

11) Profile table of adverse drug reactions not foreseeable from “Precautions”

<Analysis population>

All patients in spontaneous reporting, literature, drug use surveillance, special drug use survey, clinical trials, post-marketing clinical trials, and a clinical trial conducted by other pharmaceutical company.

<Preparation method>

Concerning the adverse drug reactions not foreseeable from “Precautions”, number of patients for each types of adverse drug reactions (SOC, PT) will be calculated based on the categories of seriousness, timing of onset, and outcome shown in Table (2). In case of several occurrences of the same adverse event/adverse drug reaction (LLT) in a given patient, they will be tabulated as one according to the priority order in 4). Events with the same PT but different LLT will be tabulated as separate events.

(5) Efficacy analysis

1) Changes in excess serum ALP

<Analysis population>

Patients included in efficacy evaluation. However, patients without baseline data or post-administration data will be excluded.

<Preparation method>

For excess serum ALP, measured value at each time point and percent change from baseline will be calculated and summary statistics and two-sided 95% confidence interval will be shown. A paired t-test will be conducted for percent change and p-value of test results will be shown. Details of handling of data at each time point will be shown in “(8) Other arrangements 5) Data of evaluation time point”.

A graph showing changes in mean \pm standard deviation will be prepared for the measured values at each time point and percent change.

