To determine tabulation and analysis that are conducted for periodic safety reporting in the survey conducted for the following purpose.

[Purpose of survey]

To observe the efficacy and safety of BENET Tablets 17.5 mg/Actonel Tablet 17.5 mg in patients with osseous Paget's disease up to Week 48 as an all-case surveillance based on the approval conditions.

2. Patients to be included in analyses

(1) Breakdown of patients to be included in analyses

“Patients included in the safety evaluation set” and “patients included in the efficacy evaluation set”.

(2) Patients included in the safety evaluation set

The patients who complete the follow-up and preliminarily fixed after approval at the patient level and do not meet the following conditions are included in the safety evaluation set.

- i) A patient not administered this drug
- ii) A patient in whom onset of adverse event is unknown
- iii) A patient found to violate the enrollment criteria after preliminary data lock
- Enrollment outside the enrollment period*

(3) Patients included in the efficacy evaluation set

Of the patients included in the safety evaluation set, those who do not meet the following conditions are excluded from efficacy evaluation and others are included in the efficacy evaluation set.

- i) Patients with all efficacy measures unknown

3. Handling of patients and data entry rules

Data entry rules and the handling of patients/data will be specified in a separately prepared document.

4. Data Lock Point

(1) Data Lock Point

Data Lock Points (DLP) are shown below.

1st: September 30, 2008

2nd: March 31, 2009

3rd: September 30, 2009

4th: March 31, 2010

5th: March 31, 2011

6th: March 31, 2012

7th: March 31, 2013

8th: September 30, 2013

9th: March 31, 2014

10th: September 30, 2014

11th: September 30, 2015

12th: September 30, 2016

13th: September 30, 2017

The date of re-examination: July 15, 2018

5. Tabulation and analysis at each DLP

(1) Patient composition diagram

- 1) number of study sites enrolling patients
- 2) number of enrolled patients
- 3) number of patients from whom CRF was collected
- 4) number of patients included in safety evaluation
- 5) number of patients included in efficacy evaluation
- 6) Tabulate the number of “patients from whom CRF was not obtained,” “patients excluded from safety evaluation,” and “patients excluded from efficacy evaluation” by reason.

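### Because the efficacy set is nested in the safety set, unknown adverse event status alone removes a patient with usable ALP from the primary endpoint analysis

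*SAP*

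**What the plan says.** The current text is SAP V4.1.

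- **Safety set, 2.(2).** Among patients with a collected CRF, "those who satisfy either of the following conditions are excluded from safety evaluation and others are included in safety evaluation". Four conditions follow: not treated, condition ii) "A patient in whom onset of adverse event is unknown", the later of a duplicate enrolment, and a start after the enrolment period.
- **Efficacy set, 2.(3).** "Of the patients included in safety evaluation, those who satisfy the following conditions are excluded from efficacy evaluation and others are included in efficacy evaluation". Its single condition is "patients from whom the information on efficacy before and after administration was not obtained".
- **Excess ALP analysis, 5.(5)1).** The population is "Patients included in efficacy evaluation. However, patients without baseline data or post-administration data will be excluded". The serum ALP, bone marker, pain and imaging analyses in 5.(5) also start from the efficacy set.
- **Protocol 8.(1).** "Conduct analysis for all patients administered this drug". No exception is made for adverse event status. Protocol 7.(5) names serum ALP as the primary endpoint.

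The nesting is not new. V2.3 of the SAP already had "Of the patients included in the safety evaluation set, those who do not meet the following conditions are excluded from efficacy evaluation", with the same condition ii) in its safety set.

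**The concern.** Not knowing whether a patient had an adverse event is a sound reason to leave that patient out of a reaction rate, because the numerator is undefined. It is no reason to discard a measured ALP, a bone marker, a pain grade or an X-ray finding. The nesting carries the exclusion across, and the SAP gives no reason for doing so. What is at stake is who enters the primary endpoint analysis: paired values can be lost for a reason unrelated to the endpoint, in a survey that the protocol sets up to analyse everyone treated.

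**Working it through.** **Step 1: apply the rules.** The plan gives no figure to reproduce here, so the check is on set membership. Under V4.1:

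- In safety set = treated AND adverse event status known AND not the later duplicate AND started within the enrolment period.
- In efficacy set = in safety set AND efficacy information before and after administration.

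Take a treated patient who is not a duplicate, started in the period, and has baseline and post-dose ALP.

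| Adverse event status | Safety set | Efficacy set | Protocol 8.(1) |
|---|---|---|---|
| Known | in | in | in |
| Unknown | out | **out** | in |

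Only the status differs between the rows, so condition ii) is sufficient by itself to remove the patient from the ALP analysis.

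**Step 2: check the meaning of condition ii).** SAP Table (2) has its own unknown category for the timing of a reaction. Condition ii) therefore most plausibly means that it is unknown whether an event occurred. If it meant an unknown date, the exclusion would be just as unrelated to ALP.

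**Step 3: look for a place where the patient comes back.**

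- 5.(1) counts exclusions by reason.
- 5.(2) lists excluded patients with the reason, but without ALP values.
- 5.(6) analyses patients excluded from safety evaluation, for adverse drug reactions only.
- 5.(7) is a line listing of all patients with a collected CRF, and it includes an entry for degree of efficacy.

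None of these is an ALP mean, interval or test.

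**Step 4: illustrate the size.** The inputs are assumptions, because the documents give no count and no ALP results. Let f be the share of ALP-evaluable treated patients removed only by condition ii), and D the absolute difference in mean percent change between kept and removed patients.

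- Shift of the reported mean = f × D
- Widening of the interval ≈ 1/√(1 − f) − 1, assuming an unchanged SD

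| f | Shift, D = 10 | D = 20 | D = 40 | Interval widening |
|---|---|---|---|---|
| 1% | 0.1 | 0.2 | 0.4 | 0.5% |
| 5% | 0.5 | 1.0 | 2.0 | 2.6% |
| 10% | 1.0 | 2.0 | 4.0 | 5.4% |
| 20% | 2.0 | 4.0 | 8.0 | 11.8% |

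Shifts are in percentage points. For example, 0.05 × 40 = 2.0 and 1/√0.95 − 1 = 0.026. The sign of the shift depends on which group has the larger fall, and the documents do not say.

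**The case against.** The strongest reply is that the affected group may be almost empty. The same investigator records adverse events and ALP on the same CRF. A patient whose adverse event status is unknown was often not seen again, so would usually have no post-dose ALP and would be excluded under 2.(3) i) or 5.(5)1) anyway. This is inference, but it is reasonable, and it stands as a limit on the size of the point.

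Nesting efficacy within safety is also a common choice, applied openly here with exclusions counted by reason. That stands too, but it does not explain why a valid ALP should be dropped.

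It can further be said that protocol 8.(1) is one general sentence, and that any workable efficacy set departs from it for duplicates, late starters and patients without data. True. Those exclusions have a plausible rationale for efficacy; condition ii) has none. The conflict with the protocol is therefore pressed only for condition ii).

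**Conclusion.** The mechanism is established from the current text: condition 2.(2) ii) alone removes a patient with usable paired data from the primary endpoint analysis, and no ALP statistic restores that patient. The number affected and the direction of any bias cannot be determined from the documents, and the effect may be small. Severity: minor.

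Several stronger readings are tempting and are not supported:

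- **The ALP result is too favourable.** This needs an assumption that the removed patients responded less well, which nothing in the documents shows.
- **The efficacy set is logically inverted.** The V2.3 sentence, read literally, does reverse its own rule. V4.1 excludes those who satisfy the condition, so this is not a current error.
- **The SAP discards dropouts against protocol 5.(4).** Neither set has a dropout exclusion. A dropout with known adverse event status and efficacy data stays in both.
- **The efficacy data vanish entirely.** The 5.(7) listing still carries an efficacy entry for each collected CRF.
- **Only 12 patients are at stake.** That figure describes pre-approval development. This survey has no fixed size.

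**What to change.** In SAP 2.(3), define the efficacy set directly: patients with a collected CRF who received this drug, are not the later of a duplicate enrolment, started within the enrolment period, and have efficacy information before and after administration. Apply condition ii) to the safety set only. The cost is one sentence and an extra branch in the 5.(1) patient composition diagram, and the efficacy set is no longer a strict subset of the safety set.

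If the nested set is kept, add a sensitivity analysis of excess ALP and ALP that includes patients excluded only under 2.(2) ii), and state the reason for departing from protocol 8.(1). The cost is one extra table, which would also show how many patients are involved.
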